4.5. Procedures for Subject Follow-up

As described in Section 4.4, subjects who permanently discontinue investigational product will be asked to attend the clinic as soon as possible. They will continue in the study for follow-up. Five weeks (± 1 week) after discontinuation of investigational product, subjects will be contacted for a follow-up by telephone. They will be asked to return to clinic according to the 8 monthly visit schedule and in addition be contacted by telephone at a time corresponding to the 4-monthly visit they would have otherwise made to replenish study medication supply. If instead of these interim telephone contacts the subject prefers to attend clinic every 4 months as originally scheduled that is an acceptable alternative.

If a subject permanently discontinues investigational product and is unable to attend visits in-person, he/she will be contacted by telephone or other methods to assess study outcomes and vital status, unless the subject has specifically withdrawn consent for all forms of contact. Follow-up of subjects who withdraw consent for contact is described below.

Every effort should be made to educate the subjects on the importance of remaining in the study and attending scheduled study visits including those required after early discontinuation of investigational product.

Other subject follow-up options to collect study outcomes and vital status should be pursued according to local laws and regulations. If one of these alternate methods to collect study outcomes and vital status is acceptable to the subject, then the subject will be deemed not to have withdrawn consent for follow-up.

4.5.1. Withdrawal of Consent for Contact

Subjects who no longer wish to attend study visits in-person will be asked to be contacted by telephone or other methods to assess study outcomes and vital status. However, if a subject specifically withdraws consent to be contacted for additional information, no further study visits or study-related telephone contacts can be conducted. Information regarding study outcomes or vital status will continue to be collected from available sources including those in the public domain. Additionally, alternative permitted options to obtain study outcomes and vital status will be reviewed based on accepted local laws and regulations. For any subject who withdraws consent for contact, the study site will be

asked to document the discussion with the subject regarding each of the contact options that were offered.

4.5.2. Subjects Deemed Lost to Follow-up

Finally, investigators should make every effort to contact subjects who are deemed lost to follow-up and who have not withdrawn consent to follow-up contacts, including pursuing any alternative contact methods permitted by local regulations. Where permitted, a third party may be used to locate alternative subject contact information that will be provided to the investigator. All attempts to contact subjects will be documented in the subject's eCRF and source notes.

Should a subject fail to attend the clinic for a required study visit, the site should attempt to contact the subject and re-schedule the missed visit as soon as possible. The site should also counsel the subject on the importance of maintaining the assigned visit schedule. In cases where the subject does not return for the rescheduled visit or cannot be reached to reschedule the missed visit, the site should make every effort to regain contact with the subject. Should the subject continue to be unreachable, then and only then will he/she be considered "Lost to Follow-up". Nonetheless, efforts to attempt to locate and contact the subject will continue until the study end.

5. STUDY TREATMENTS

5.1. Investigational Product and Other Study Treatment

Albiglutide (and albiglutide matching placebo) will be provided as a fixed-dose, fully disposable pen injector system for delivery of the investigational product (albiglutide or albiglutide matching placebo) from a prefilled dual chamber glass cartridge that is an integral part of the pen. The pen is intended for single use by the subject. It is designed for manual reconstitution of the dose, priming and insertion of the pen needle, and manual injection by the subject.

Albiglutide (or albiglutide matching placebo) is intended for self-administration as a subcutaneous injection in the abdomen, thigh or upper arm region. Rotation of use of injection sites is recommended. Albiglutide and insulin may be injected in the same body region but the injections should not be adjacent to each other. The albiglutide pen includes a mechanical locking system that prevents the user from manipulating the dose button before the cartridge has been fully reconstituted. Reconstitution is performed through rotation of the pen housing parts. The pen is designed to work with standard pen needles.

When the injector pen product is reconstituted by the subject, a neutral, isotonic solution is produced. Separate pens are required to deliver either 30 mg of albiglutide, 50 mg of albiglutide, or matching placebo in a 0.5-mL injection volume.

The contents of the label will be in accordance with all applicable regulatory requirements.

Under normal conditions of handling and administration, investigational product is not expected to pose significant safety risks to site staff. Take adequate precautions to avoid direct eye or skin contact and the generation of aerosols or mists. Notify the monitor of any unintentional occupational exposure. A Material Safety Data Sheet (MSDS) describing the occupational hazards and recommended handling precautions will be provided to site staff if required by local laws or will otherwise be available from GSK upon request.

The investigational product (albiglutide and albiglutide matching placebo) must be stored in a secure area at 2°C to 8°C and protected from freezing. Each site must maintain a temperature log. Access to and administration of the investigational product will be limited to the investigator and authorised site staff (investigator or designee). Investigational product must be dispensed or administered only to subjects enrolled in the study and in accordance with the protocol.

Procedures for the disposal of unused study treatment will be provided in the SRM.

Investigational product (albiglutide or albiglutide matching placebo) will be administered once weekly by subcutaneous injection. The first dose is to be administered at the clinic. The starting dose of albiglutide will be 30 mg once weekly. If at any stage after 5 weeks of treatment in the opinion of the investigator the subject needs to have intensified therapy to improve glycaemic control, the dose of investigational product should be increased before altering the doses of other glucose-lowering medication. In this case the subject will be called in for an unscheduled visit to supervise an increase in dose from 30 mg to 50 mg. Subjects randomly assigned to albiglutide matching placebo will also go through the increased dose procedure to maintain study blind. If a subject experiences tolerability issues with the higher, 50mg dose then the investigator may decrease the dose back to 30 mg without the need for an unscheduled visit to supervise down titration, other than for the subject to collect pens of the correct dose.

Albiglutide (or albiglutide matching placebo) may be administered at any time of day without regard to meals. Preferably, it should be administered once a week on the same day each week. The day of weekly administration can be changed if necessary as long as the last dose was administered 4 or more days previously. If a dose is missed, it should be administered as soon as possible within 3 days after the missed dose. Thereafter, subjects can resume dosing on their usual day of administration. If it is more than 3 days after the missed dose, subjects should wait and administer their next regularly scheduled weekly dose.

If a subject misses 4 or more consecutive doses, the investigator should contact the medical monitor to discuss options for helping assure better compliance.

5.2. Treatment Assignment

Subjects will be assigned to study treatment in accordance with the randomisation schedule.

Randomised treatment assignment will be done via the Interactive Voice Response System (IVRS), and randomisation will be implemented based on a sequestered fixed randomisation schedule. Study centre personnel will call the IVRS once a subject has met all prerequisites for randomization; the IVRS will assign treatment.

Blinded study centre personnel will receive a randomisation notification indicating only the unique subject identifier and the date and time of randomisation. Each subject number will be a unique identifier. Once a subject number has been assigned, the number will not be reused even if the subject withdraws before receiving any investigational product. Details of the treatment assignment process are contained in the SRM.

5.3. Blinding

This is a double-blind study, neither the subject nor the study physician will know which of the two treatments (albiglutide or placebo) the subject is receiving.

The investigator or treating physician may unblind a subject's treatment assignment **only in the case of an emergency or in the event of a serious medical condition, when knowledge of the study treatment is essential for the appropriate clinical management or welfare of the subject, as judged by the investigator**. Investigators have direct access to the subject's individual study treatment. It is preferred (but not mandatory) that the investigator first contacts the GSK Medical Monitor or appropriate GSK study personnel to discuss options **before** unblinding the subject's treatment assignment. If GSK study personnel are not contacted before the unblinding, the investigator must notify GSK as soon as possible after unblinding, but without revealing the treatment assignment of the unblinded subject, unless that information is important for the safety of subjects currently in the study. The date and reason for the unblinding must be fully documented in the appropriate data collection tool.

If a subject is unblinded by the investigator or treating physician then discontinuation of investigational product treatment for that subject will be at the discretion of the investigator. However, the subject should continue to be followed in the study (see Section 4.5).

GSK's Global Clinical Safety and Pharmacovigilance (GCSP) staff may unblind the treatment assignment for any subject with an SAE. If the SAE requires that an expedited regulatory report be sent to one or more regulatory agencies, a copy of the report, identifying the subject's treatment assignment, may be sent to clinical investigators in accordance with local regulations and/or GSK policy.

5.4. Product Accountability

In accordance with local regulatory requirements, the investigator, designated site staff, or head of the medical institution (where applicable) must document the amount of investigational product dispensed and/or administered to study subjects, the amount returned unused by study subjects, and the amount received from and returned to GSK, when applicable. Product accountability records must be maintained throughout the course of the study.

5.5. Treatment Compliance

Subjects will be instructed to return all unused and used injector pens at the visits specified in the Time and Events Table (Table 1) in order to perform drug accountability and determine compliance. Subjects will be provided with a sharps container for the disposal of used pens. To comply with health and safety considerations there will be no count made of used pens; only returned unused pens will be counted. In addition, subjects will be provided with a pre-printed card at each dispensing visit to record the date of each dose. The card is to be returned at the next dispensing visit with the unused pens.

5.6. Concomitant Medications and Non-Drug Therapies

5.6.1. Permitted Medications and Non-Drug Therapies

The usual care provider will manage the subjects according to standard of care, following local prescribing information. Close adherence to professional society guidelines for standard of care therapies in type 2 diabetes and cardiovascular disease will be emphasized during study conduct. Standard of care is described in greater detail in Section 3.2.

Unless specified as a prohibited medication in Section 5.6.2, all concomitant medications should be considered permitted provided they are not contraindicated for the individual subject concerned.

Like other members of the class, albiglutide causes a delay in gastric emptying, and thereby has the potential to impact the absorption of concomitantly administered oral medications. This should be taken into account by investigators when prescribing concomitant medication.

It may be necessary to reduce the dose of concomitantly administered insulin secretagogues (such as SUs) or insulin to reduce the risk of hypoglycaemia when starting albiglutide.

All concomitant anti-hyperglycaemic medications (name of agent, total daily dose, start and stop dates) will be recorded in the eCRF at each visit. Concomitant cardiovascular medications taken during the study will also be recorded at each visit by class of agent. Additionally, all medications used within the 30 days prior to the onset and throughout the duration of an SAE, AE of special interest (Section 6.2.3), or an AE leading to discontinuation of investigational product will be recorded as individual agents, reason for use, together with start dates (and stop dates if applicable) and any changes since any previous AE.

5.6.2. Prohibited Medications and Non-Drug Therapies

Subjects may not take a GLP-1 receptor agonist (other than blinded investigational product), nor any investigational drug, during the study (and any follow-up period after discontinuing investigational product).

If a subject receives a prohibited medication, a protocol deviation will be recorded.

5.7. Treatment after the End of the Study

Following the final study visit subjects will be contacted by telephone 5 ± 1 weeks after last dose of study medication to assess any AEs ongoing since the last visit or newly emergent.

Subjects will be treated as deemed appropriate by the investigator following the end of the study. Investigational product will not be provided to subjects by GSK after the end of the study.

The half-life of albiglutide is approximately 5 days, and significant therapeutic concentrations can persist for 3 to 4 weeks after discontinuation. The choice of other medicinal products and dose selection should be considered accordingly, as adverse reactions may continue and efficacy may, at least partly, persist until albiglutide levels decline.

The investigator is responsible for ensuring that consideration has been given to the post-study care of the subject's medical condition whether or not GSK is providing specific post study treatment.

5.8. Treatment of Study Treatment Overdose

No data are available with regard to albiglutide overdose in humans. The highest recommended dose of albiglutide is 50 mg once weekly.

During clinical studies of subjects with type 2 diabetes, the highest dose of albiglutide administered was 100 mg subcutaneously every four weeks for 12 weeks. This dose was associated with an increased frequency of nausea, vomiting, and headache.

There is no specific antidote for overdose with albiglutide. In the event of a suspected overdose, the appropriate supportive clinical care should be instituted, as dictated by the subject's clinical status. Anticipated symptoms of an overdose may be severe nausea, vomiting or headache. A prolonged period of observation and treatment for these symptoms may be necessary, taking into account the half-life of albiglutide (5 days).

6. STUDY ASSESSMENTS AND PROCEDURES

The schedule of study assessments is shown in [Table 1](#). Detailed procedures for each assessment are provided in the SRM.

Table 1 Time and Events Table

| Procedures ^{1,2} | Screening ³ | Randomization ³ /Baseline (can be same day as Screening Visit) | Study Drug Check Phone Call (4-6 wks post rand.) | Clinic Visit Month 4 ± 18 days then every 8 months ± 18 days throughout the study | Unscheduled dose adjustment visit (if warranted) | Clinic Visit Month 8 ± 18 days then every 8 months ± 18 days throughout the study | Final study clinic visit ⁴ (or early withdrawal) | Follow up Phone Call 5 ± 1 weeks after last IP dose |
|--|------------------------|--|---|--|---|--|--|---|
| Written informed consent | X | | | | | | | |
| Review of Inc/excl criteria | X | X | | | | | | |
| Demography & directed medical history | X | | | | | | | |
| Assessment of MACE and micro-vascular events | | | | X | | X | X | |
| HbA1c | X ⁵ | | | X | | X | X | |
| Serum creatinine (eGFR) | X ⁵ | | | | | X | X | |
| Liver Function Tests ⁶ | | X | | | | X | X | |
| Genetic sampling ⁷ | | X | | | | | | |
| Patient reported outcomes questionnaires ⁸ | | X | | | | X | X | |
| Key concomitant non-diabetes medication | | X | | X | | X | X | X |
| Diabetes medication | | X | | X | | X | X | X |
| Study drug reminder | | | X | X | X | X | | |
| Physical examination ⁹ | | X | | | | X | X | |
| SAEs, AEs of special interest, AEs leading to IP discontinuation | | X | X | X | X | X | X | X |
| Pregnancy test ¹⁰ | X | X | | | | | | |
| Study drug dispense/compliance ¹¹ | | X | | X | X | X | X | |

- Subjects who discontinue investigational product should be handled as described in Section 4.4 and Section 4.5.
- Assessments per the Month 4 visit will alternate with those per the Month 8 visit throughout the study i.e., assessments at months 4, 12, 20 etc will be per Month 4; those at month 8, 16, 24 etc..will be per Month 8.
- Screening and Randomisation can occur at the same visit if all eligibility information is available. If Screening and Randomisation occur at the same visit assessments should not be duplicated.
- Once it is projected that the target number of MACE events will have been collected, a 3 month window will be defined for conducting the final, face to face visit.
- HbA1c and creatinine assessed using local laboratories at Screening visit and measured no more than 6 months prior to randomisation. If HbA1c or creatinine have not been assessed in the previous 6 months assessments to be performed via a central laboratory and results available prior to randomization. The investigator has the discretion to repeat screening HbA1c, and/or creatinine, based on clinical rationale even if previously available local results meet the eligibility criteria to allow the investigator to accommodate the possibility of change between screening and randomisation.
- Liver function tests: ALT, AST, alkaline phosphatase, bilirubin, GGT. Blood samples for LFTs at randomization must be collected prior to the first dose of investigational product.
- Informed consent for genetic research must be obtained before collecting a sample. Genetics sample can be collected at any time after genetic consent has been obtained and the subject has been randomised.
- TRIM-D, EQ-5D and study specific questionnaire (details in Section 6.3).
- See Section 6.2.7.
- Only applies to women of child bearing potential. At screening perform urine pregnancy test. If positive, send serum sample to the central laboratory for confirmation. At Randomisation perform a urine pregnancy test. If result is positive do not randomize the subject. If the urine pregnancy test is negative then the subject can be randomised. If Screening and Randomisation are to take place at the same visit then follow the instructions for Screening. See Section 6.2.6.
- Study drug dispensing not performed at final visit, compliance check not performed at Randomisation.

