This study is designed with minimal intervention above normal clinical care of subjects with type 2 diabetes, whilst allowing thorough evaluation of cardiovascular and other events of special interest (Section 6.2.3), thus investigating the safety of albiglutide in the typical clinical situation. Sites will employ pre-screening to assess potential subjects for study entry. Screening and randomisation can then occur at the same visit or in close proximity depending on scheduling. Contact with subjects will be every four months after the randomisation visit. HbA1c will be measured at 4 month clinic visits. Serum creatinine and liver function tests (LFTs) will be measured and a targeted physical assessment performed at 8 month clinic visits (Table 1).

The study will be event driven, i.e., follow up will continue until it is projected that approximately 611 adjudicated MACE events will have occurred. Consequently, the maximum duration of the study for an individual participant is dependent both on the time taken for recruitment and the MACE event rate, and is estimated to be between 3 and 5 years. If the observed rate for MACE is 2.0% or 3.0%, the mean follow-up will be 3.2 or 2.2 years, respectively.

An Executive Committee will be the main decision-making body for the study, in collaboration with the Sponsor (GSK). It is charged with the overall scientific, professional and operational conduct of the study. Amongst other roles pre-specified in

its Charter, the Executive Committee will ensure proper study conduct and conformance to the protocol, consider and agree changes to the protocol based on emerging scientific and/or clinical advances (e.g., new emerging data with other GLP-1 receptor agonists), advise on the selection of study sites and assist in subject recruitment strategies.

An IDMC will have study oversight to ensure participant safety and scientific integrity of the data (Section 9.8), an independent Cardiovascular Endpoint Committee (CEC) blinded to treatment allocation will adjudicate cardiovascular outcome events (Section 6.2.1) and a Pancreatitis Adjudication Committee will adjudicate potential events of pancreatitis.

Subject completion is defined as completion of all periods of the study up to and including any follow-up period.

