6.2.2. Adverse Events (AE) and Serious Adverse Events (SAEs)

The definitions of an AE or SAE can be found in [Appendix 5](#).

The investigator or site staff will be responsible for detecting, documenting and reporting events that meet the definition of an AE or SAE.

For this study events of myocardial infarction, stroke, unstable angina requiring urgent revascularization, hospitalization for heart failure, TIA and sudden cardiac death will not be collected or reported as AEs or SAEs. These events will be collected separately, subjected to blinded adjudication by an independent CEC using prespecified diagnostic criteria, and reported separately (Section 6.2.1.1). All other events that meet serious criteria as defined in [Appendix 5](#) should be reported as SAEs.

All events with an outcome of death will be adjudicated to classify the cause of death as specifically cardiovascular or non-cardiovascular. Any event resulting in death should be reported as a SAE unless the event is myocardial infarction, stroke, unstable angina w/ urgent revascularization, Heart failure, TIA or sudden cardiac death which the protocol specifies are not to be collected as adverse events.

The study will not collect all non-serious AEs. Non-serious AEs leading to discontinuation of investigational product and non-serious AEs of special interest (see Section 6.2.3) will be collected.

Any events not specifically addressed above should be reported as an AE or SAE according to the definitions in [Appendix 5](#).

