8.3.2. Analysis Data Set

For time to event data, censoring time for subjects who lost to follow-up is defined as following:

- For primary analysis, subjects who are lost to follow-up will be censored at the date of last evidence of confirmatory status for MACE events.
- For on-treatment analysis, censoring date will be the last dose date.
- For on-therapy analysis (on-treatment+56 days), censoring date will be the last dose date+56 days.
- For analysis of all cause of mortality, censoring date will be the latest date known alive.

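### For subjects on drug until the final visit, no scheduled assessment covers non-fatal MACE or other CEC events in the 4-6 weeks after the last dose

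*Protocol*

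**What the plan says.** **Schedule.** In Table 1 (Section 6) the MACE row reads "Assessment of MACE and micro-vascular events | | | | X | | X | X", with nothing in the last column, which is headed "Follow up Phone Call 5 ± 1 weeks after last IP dose". The safety row is marked in that column: "SAEs, AEs of special interest, AEs leading to IP discontinuation | | X | X | X | X | X | X | X". The amended Table 1 listed under Amendment 2 (Appendix 9, Section 11.9.2) keeps the blank. The Amendment 2 table for subjects who stop drug early is also blank at this call, but it marks MACE assessment at their later telephone contacts, clinic visits and final visit.

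**Purpose of the call.** Section 5.7 says it is "to assess any AEs ongoing since the last visit or newly emergent".

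**Exclusion from AE and SAE reporting.** Section 6.2.2 lists MI, stroke and unstable angina requiring urgent revascularisation, and continues: "hospitalization for heart failure, TIA and sudden cardiac death will not be collected or reported as AEs or SAEs". It then says that these events are collected separately and adjudicated by the CEC. Section 6.2.1 requires potential endpoints to be entered in the eCRF with source documents.

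**Time windows.** Section 6.2.2.1 runs AE and SAE collection up to the follow-up contact; no such period is given for CEC events. Section 3.1 states: "Subject completion is defined as completion of all periods of the study up to and including any follow-up period". Section 8.3.6.1 defines the primary analysis over the full study duration and repeats it on events up to 56 days after the last dose. For that on-therapy analysis, Section 8.3.2 says the "censoring date will be the last dose date+56 days".

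**The concern.** The last scheduled contact asks for a category of event from which the trial's own cardiovascular endpoints have been removed. A subject who takes drug up to the final visit and has a non-fatal MI two weeks later meets no scheduled question about it. Section 5.7 notes that therapeutic concentrations can last 3 to 4 weeks after stopping, so part of this interval is still exposed time in a cardiovascular safety trial.

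Two things are at stake. One is complete ascertainment of MI, stroke and heart-failure hospitalisation during washout. The other is the on-treatment plus 56 days analysis, whose window runs beyond the last scheduled MACE check. Person-time there can be counted while events are recorded only if a site volunteers them, which would lower the incidence per 100 person-years and the absolute risk difference.

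**Working it through.** **1. The plan's own figures.** Inputs from Section 8.2.1: margin 1.3, true hazard ratio 1.0, one-sided 0.025, power 90%; 1:1 allocation from Section 3.1.

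Events = 4 × (1.960 + 1.282)² / (ln 1.3)² = 611 after rounding up. Power at 611 events is 90.0%. The stated target is reproduced.

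Mean follow-up = 611 / (9400 × rate): 3.25 years at 2.0% and 2.17 years at 3.0%, against the stated 3.2 and 2.2.

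**2. Who falls in the gap.** Early discontinuers have later MACE assessments, so the gap concerns subjects on drug until the final visit. Event-free subjects: 9400 − 611 = 8789. This treats all of them as alive and retained, so it is an upper figure. The protocol does not give the share still on drug; I assume 70-100%.

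**3. Expected first MACE up to a 5-week call.**

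- Person-years: 8789 × 0.7 × 5/52.18 = 590, to 8789 × 1.0 × 5/52.18 = 842.
- Events: 590 × 0.02 = 12, to 842 × 0.03 = 25. Against 611 this is 2-4%.
- Wider assumptions (4-6 weeks, 60-100% on drug, same rates): 8789 × 0.6 × 0.02 × 4/52.18 = 8, to 8789 × 0.03 × 6/52.18 = 30.

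**4. Effect on the primary test.** The event target does not depend on the call. Counting all 30 extra events would give 641 and raise power from 90.0% to about 91.3%.

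**5. The 56-day window.**

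- Person-years: 8789 × 0.7 × 56/365.25 = 943, to 8789 × 56/365.25 = 1348.
- Events: 943 × 0.02 = 19, to 1348 × 0.03 = 40.
- The call falls on days 28-42, so 56 − 42 = 14 to 56 − 28 = 28 days of the window lie beyond it even if MACE were asked at the call.
- Upper bound on dilution: if every subject stayed on drug and no event in the window were recorded, the added 0.153 years would be 0.153/(3.2 + 0.153) = 4.6% to 0.153/(2.2 + 0.153) = 6.5% of on-therapy time. Absolute rates would be understated by about that proportion in each arm.

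**The case against.** The strongest reply is that the event, not the visit, triggers recording. Sections 6.2.1 and 6.2.2 give an eCRF and CEC route that is not tied to any Table 1 column. Section 6.2.2.2 suggests an open question about medical problems since the last contact, and the call covers newly emergent events. An MI mentioned there has a form and an adjudication path. This stands: a reader might infer that such events are captured nowhere, and the documents do not support that. What is missing is the prompt and an end date.

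It can also be said that primary follow-up ends at the final visit. Sections 4.4.2 and 4.4.4 follow subjects who stop drug until that visit, and the call is described under a heading on treatment after the end of the study. This points to the final visit as the cut-off, although no sentence says so for completers, and the Section 3.1 definition of completion includes follow-up. Details of completer censoring may sit in an analysis plan that is not shown.

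The 56-day rule in Section 8.3.2 is introduced as a rule for subjects lost to follow-up. That is fair, but Section 8.3.6.1 sets the same 56-day window for the sensitivity analysis generally, with no cap at the last MACE assessment.

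Two further inferences fail. A reader might think that uncounted events favour non-inferiority. The schedule is blinded and identical in both arms; equal under-capture leaves the expected hazard ratio essentially unchanged and widens its interval. A reader might also think that fatal events are picked up and non-fatal ones are not. Section 6.2.2 excludes fatal MI, fatal stroke and sudden cardiac death from SAE reporting too, so they rely on the same route.

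**Conclusion.** The point holds as a gap in scheduled ascertainment. For subjects on drug until the final visit, no scheduled assessment covers non-fatal MACE or other CEC events in the 4-6 weeks after the last dose, and capture through the separate route is left to site initiative. The primary test, the 611-event target and the expected hazard ratio are essentially unaffected.

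The size is about 12-25 expected first MACE over 5 weeks, resting on an assumed 70-100% of event-free subjects on drug, annual rates of 2-3%, and no allowance for other deaths or loss. These are events at risk of being missed, not events shown to be missed. Absolute rates in the on-treatment plus 56 days analysis may be understated, by about 5-7% at the very most.

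**What to change.** 1. Mark MACE assessment at the 5 ± 1 week call in both Time and Events tables, and send any event reported there to the CEC.
2. State the date on which collection of CEC events ends and the date on which primary follow-up ends.
3. Censor the on-therapy analysis at the earlier of last dose + 56 days and the last MACE assessment. The first change alone does not suffice, because a call at days 28-42 cannot cover 56 days.

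The cost is a table and wording change in an amendment. The call is already made, so the only added work is a few extra adjudications. The sample size and event target stay as they are.
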